“What is the effect of NSPT on the clinical periodontal parameters and its correlation to changes in GCF levels of Endocan and TNF- α in hypertensive periodontitis patients compared to non-hypertensive patients?”

PICOTS Elements:	
Patient/Problem	Stage II periodontitis patients with controlled hypertension.
Intervention	Non-Surgical periodontal therapy.
Comparator	Stage II periodontitis healthy individuals.
Outcome	-Clinical evaluation as a primary objective. -Biochemical evaluation as secondary objective. -Blood pressure measurement as secondary objective.
Time	-Baseline and 3 months (for clinical evaluation) -3 months (for biochemical analysis) -3 months (for blood pressure evaluation)
Setting	Faculty of Dentistry, Ain Shams University.

IV. Aim of the Study:

- 1- To correlate changes in GCF level of Endocan and TNF- α with changes in periodontal parameters after NSPT in both groups with clinical parameters.
- 2- The aim of the present study is to investigate changes in the levels of Endocan and TNF- α in stage II periodontitis patients with controlled hypertension in comparison to healthy subjects before and after NSPT.
- 3- To correlate blood pressure changes before and after NSPT.

Primary outcome:

Clinical evaluation of periodontal parameters plaque Index, gingival index, probing depth and clinical attachment level comparing between hypertensive and non-hypertensive groups.

Secondary outcome (s):

- Biochemical evaluation of GCF levels of Endocan and TNF- α in hypertensive and healthy subjects by ELISA.
- Systolic and Diastolic Blood pressure measurements before and after NSPT in hypertensive vs healthy individuals and check if NSPT reduces SBP and DBP.

Clinical Relevance:

To understand the role of NSPT in stabilizing the periodontal condition as well as reduce GCF levels of Endocan and TNF- α which will subsequently result in better hypertension control and improve the lifestyle.

V. Hypothesis:

Hypertension influences response to NSPT and GCF levels of Endocan and TNF- α .

VI. Ethical considerations

•Risk and discomfort of patients: This research will be conducted with considerations of patients' safety and with attempts to reduce patients' discomfort by reassurance.

•Minimization of the risk: Patients' baseline vitals will be taken before any clinical intervention to ensure patients' safety. Moreover, all medical operations will be conducted under standardized infection control

procedures.

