2. A calibrated standard aneroid sphygmomanometer. The average of 3 blood pressure values (systolic blood pressure SBP and diastolic blood pressure DBP), will be taken at 1 minute interval, this will be used in data analyses.

(2020 International Society of Hypertension Global Hypertension Practice Guidelines)

3. For all patients who are suitable for the study the following clinical evaluation parameters will be measured:
 - a) Plaque index (PI) (Silness&Löe, 1964)
 - b) Gingival index (GI) (Löe&Silness, 1963)
 - c) Probing depth (PD) (Caton, 1980).
 - d) Bleeding on probing (BOP) (Ainamo, 1985)
 - e) Clinical attachment level (CAL) (Ramfjord, 1967).
 - f) Standardized periapical radiograph. (Pananou, 2017)

Note: Full mouth assessment will be done and then the deepest site will be evaluated for the GCF sample.

4. Baseline GCF samples will be taken the day after patients were clinically evaluated to prevent contamination with blood related to the probing of inflamed areas.
5. The sample areas will be insulated with cotton rolls to prevent saliva contamination and all supragingival plaque will be eliminated. The paper strips will be placed into the periodontal pocket and then permitted to remain for 30 seconds.
6. All patients will undergo full mouth NSPT, this will be done using ultrasonic and hand instruments.
7. The patients will receive oral hygiene instructions including tooth brushing using modified bass technique. All patients will be provided with toothbrush (soft), toothpaste (signal) and interdental cleaning with dental floss or interdental brush.
8. Two weeks follow-up to ensure that appropriate oral hygiene instructions are followed. The clinical parameter to be assessed will be PI and BOP, patients with PI 2 and BOP $> 10\%$ will be eliminated from the study.
9. Then clinical evaluation, collection of samples and measuring of SBP and DBP will be performed at 3 months after NSPT in both groups.

Outcomes Assessment:

- Clinical assessment.
- Biochemical assessment.
- Blood pressure measurement.

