For clinical assessment the following clinical parameters including PI, GI, PD, BOP and CAL will be recorded for each individual at 1 site at baseline and 3 months postoperatively. Clinical parameters of PI and BOP will be assessed at 2 weeks, 4 weeks and 6 weeks follow ups to ensure proper oral hygiene. Regarding biochemical analysis, GCF samples will be collected preoperative and 3 months after NSPT. Blood pressure measurements will be taken before and after 3 months of NSPT.

a) Clinical Assessment

The following clinical parameters will be taken using UNC15 Probe at baseline and 3 months postoperative.

- **Plaque index: - (Loe and Silness ,1963)**
0 = no plaque.
1 = plaque recognized only by running a probe across the tooth surface.
2 = plaque visible to the naked eye.
3 = abundance of soft matter.
- **Gingival index: -(Loe and Silness ,1963)**
0 = Normal gingiva
1 = Mild inflammation – slight edema. No bleeding on probing
2 = Moderate inflammation -redness, edema and glazing.
Bleeding on probing.
3 = Severe inflammation – marked redness and edema.
Ulceration. Tendency for spontaneous bleeding
- **Probing depth : (Ramfjord, 1959)**
Will be measured from the gingival margin to the depth of the pocket at four points (mesio-facial, mid-facial, disto-facial and mid-lingual) to the nearest millimeter using UNC-15 periodontal probe The average of the three facial points will be recorded as the facial probing depth (FPD), while the mid-lingual point will be recorded as the lingual probing depth.
- **Clinical attachment level (CAL):(Ramfjord et al., 1975).** Will be measured from the CEJ to the depth of the periodontal pocket.

b) Biochemical Assessment:

Biochemical assessment will be done at the deepest pocket at baseline, and 3 months after non-surgical periodontal therapy. Endocan and TNF- α levels will be determined using commercial human Endocan (ESM-1) and TNF- α ELISA Kits. Measurements will be performed according to the manufacturer's instructions.

c) Blood Pressure measurement:

Blood pressure measurement will be done according to, 2020 International Society of Hypertension Global Hypertension Practice Guidelines.

IX. Statistical Analysis

The obtained results will be collected, tabulated, and subjected to appropriate statistical analysis.

X. Funding of the Study

This study will be personally funded by the researcher.

References:

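### The primary clinical outcomes are recorded at one unnamed site per patient although the whole mouth is charted and treated; this is imprecise and, if the site is the deepest, adds regression to the mean to the before-after change

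*Protocol*

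**What the plan says.** Section IV (Primary outcome) sets the primary outcome as "Clinical evaluation of periodontal parameters plaque Index, gingival index, probing depth and clinical attachment level comparing between hypertensive and non-hypertensive groups". Section VIII, Outcomes Assessment, then fixes how the data are collected: "PI, GI, PD, BOP and CAL will be recorded for each individual at 1 site at baseline and 3 months postoperatively".

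The site is not identified there. The protocol selects a site in two places, both for the biomarkers:

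- The note to step 3 of the study procedures: "Full mouth assessment will be done and then the deepest site will be evaluated for the GCF sample".
- Outcomes Assessment, part b: "Biochemical assessment will be done at the deepest pocket at baseline, and 3 months after non-surgical periodontal therapy".

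Three other statements bear on the unit of measurement:

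- Probing depth is taken "at four points (mesio-facial, mid-facial, disto-facial and mid-lingual) to the nearest millimeter using UNC-15 periodontal probe". The three facial readings are averaged into a facial depth and the lingual reading is kept separate.
- Step 6 gives NSPT to the full mouth.
- Step 8 uses bleeding on probing as a percentage, with a 10% threshold, in its two-week compliance check ("patients with PI 2 and BOP" ...).

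The research question in Section III opens with "What is the effect of NSPT on the clinical periodontal parameters". Aim 1 in Section IV is "To correlate changes in GCF level of Endocan and TNF- α with changes in periodontal parameters after NSPT in both groups".

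**The concern.** The therapy treats the whole mouth and the baseline charting covers it, but the outcome section reduces each patient to one site. Two consequences follow.

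**Precision.** A single location carries the full probing and rounding error. PI and GI become a single 0-3 score. With 20 patients per group, this noise goes straight into the primary comparison, wherever the site lies.

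**Regression to the mean.** If the clinical site is the deepest one, it was chosen because its reading was the largest of at least 80. Part of that excess is measurement error, so the site tends to read shallower next time even if nothing has changed. No second baseline probing is described, so the reading that selects the site would also be its baseline value. Both groups receive NSPT, so no arm can separate this fall from a treatment response.

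This is a rule about data collection. If only one site is recorded at 3 months, no analysis plan can recover a full-mouth change afterwards.

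**Working it through.** **Inputs from the protocol.** At least 20 teeth (inclusion criterion 3); 4 points per tooth, to the nearest mm, with three facial points averaged (Outcomes Assessment); 20 patients per group. Points available: 20 × 4 = 80 at minimum, and 28 × 4 = 112 for 28 teeth.

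**Assumed inputs, because the protocol gives none.** Mean PD 3 mm, true between-site SD 0.8-1.0 mm, probing-error SD e = 0.4-0.8 mm, errors independent between points and visits.

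The protocol states no figure on this point, so there is none to reproduce.

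**Step 1: re-measurement noise by hand.** One reading has error variance e² plus about 1/12 mm² from rounding to 1 mm. For the change in a mean of k points:

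SD(change) = √[2(e² + 1/12) / k]

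| Measure | k | e = 0.4 mm | e = 0.8 mm |
|---|---|---|---|
| one point | 1 | √0.487 = 0.70 | √1.447 = 1.20 |
| facial average, one tooth | 3 | 0.40 | 0.69 |
| full-mouth mean, 20 teeth | 80 | 0.08 | 0.13 |
| full-mouth mean, 28 teeth | 112 | 0.07 | 0.11 |

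Simulation with the actual rounding agrees: 0.65-1.1 mm when the one point is the deepest, 0.40-0.72 mm for the facial average at one tooth, and 0.07-0.14 mm for the full-mouth mean. By the formula, one location is noisier than the full-mouth mean by a factor between √(80/3) = 5.2 and √112 = 10.6.

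**Step 2: with variation in response added.** In an illustrative model (80 points, between-site SD 1.0 mm, mean reduction 1 mm varying by site with SD 0.8 mm and by patient with SD 0.3 mm, e = 0.5 or 0.8 mm), the SD of change was 1.17-1.40 mm at the deepest point and 0.33-0.34 mm for the full-mouth mean. With 20 per group the standard error of the difference is SD × √(2/20) = 0.316 × SD. That is 0.37-0.44 mm against 0.10-0.11 mm.

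**Step 3: regression to the mean with no treatment effect.** Every point is probed twice, the location is selected on the first probing, and the second reading is compared with it.

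| What is followed | Spurious fall in PD |
|---|---|
| the deepest point itself | about 0.5-1.5 mm |
| facial average at the tooth holding the deepest point (within-tooth correlation 0 or 0.5) | about 0.1-0.4 mm |
| facial average at the tooth where that average is highest | about 0.2-0.7 mm |
| full-mouth mean | 0.00 mm |

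Widening the inputs for the deepest point (between-site SD 0.8-1.2 mm, e = 0.3-0.8 mm, 80 or 120 points) gives 0.32-1.54 mm. For scale, Section II describes stage II as CAL 3-4 mm.

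**Step 4: the between-group comparison.** Following the deepest of 80 points, with 20 per group, the same true 1 mm reduction in both groups and a two-sided 5% t-test:

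| Spread and error in the two groups | Type I error | Bias |
|---|---|---|
| alike (between-site SD 1.0 mm, e = 0.5 mm) | 5.1% | about 0 |
| between-site SD 1.0 vs 1.3 mm | 7.5% | 0.11 mm |
| e = 0.5 vs 0.8 mm | 55% | 0.63 mm |

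The artefact cancels in the first row. The other two rows show what it would take to break that.

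**The case against.** The strongest reply is that the deepest site is designated only for GCF. A reader might infer that the clinical outcomes are taken there too, since no other site is ever selected, but no sentence says so. This stands: regression to the mean is conditional on that inference. The reply does not rescue the passage, because a one-site outcome with no rule for choosing the site is itself a gap, and the loss of precision applies to any site.

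A reader might also infer that the primary comparison is biased. The documents do not support that. Both groups share the same site rule, treatment and visits, so the artefact largely cancels. The 55% figure needs probing error to differ between groups, and nothing in the protocol suggests that it does.

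A third inference would be that CAL, PI and GI are inflated by the same amounts as PD. Selection is on depth, so these measures regress only as far as they correlate with PD at that site. They were not simulated.

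The facial averaging matters as well. If the recorded PD is the facial average, the artefact is 0.1-0.4 mm at the tooth holding the deepest point, and the 0.5-1.5 mm range does not apply.

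The BOP percentage rule is a compliance check and BOP is not a primary outcome. It shows that the protocol is inconsistent about the unit of measurement, and no more.

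Finally, a site-matched clinical reading is sensible for aim 1, and without an untreated arm even a full-mouth mean does not isolate the effect of NSPT. Both points are right. They argue for keeping the deepest site in its own role and for cautious wording of within-group results. They do not argue for a single-site primary outcome. A repeat baseline reading or baseline adjustment could reduce the artefact at the deepest site, but would not give a measure of the whole mouth.

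**Conclusion.** The point holds in this form. The primary clinical outcomes are tied to one unnamed site per patient, which does not match the full-mouth charting and therapy in the same protocol.

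The firm consequence is imprecision: a re-measurement SD of PD change of about 0.4-1.1 mm at one site, against 0.07-0.14 mm for the full-mouth mean. The conditional consequence, if the site is the deepest and its selecting reading is its baseline, is a spurious within-group fall in PD of about 0.5-1.5 mm for the deepest point or 0.1-0.4 mm for the facial average at that tooth. That would contaminate the before-after answer to the research question. It does not by itself invalidate the between-group test.

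All these sizes rest on assumed SDs and on independent errors between sites. An examiner shift common to all sites at a visit would not average out, so it would narrow the advantage of the full-mouth mean. Within the ranges tried the direction does not change. This is a cheap improvement rather than a fatal flaw.

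**What to change.** - In Section IV (Primary outcome) and Section VIII (Outcomes Assessment), define the primary clinical outcomes as full-mouth patient-level means of PI, GI, PD and CAL. Chart them at baseline and again at 3 months by the same examiner. Report BOP as a percentage of sites, as a supporting measure.
- Replace the one-site wording. Name the baseline-deepest site as the site for GCF and for the site-matched correlation in aim 1, and say whether PD there is the point reading or the facial average.
- State that within-group change at that site includes regression to the mean and will not be reported as the effect of NSPT.

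The cost is a change of wording and some minutes of extra charting at 3 months for 40 patients; the baseline charting is already planned. The downside is that the average change across the mouth will be smaller in millimetres than the change at the deepest site.

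### The PD recording rule averages the three facial readings, so for a facial pocket the PD change in aim 1 is not that of the point sampled for GCF

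*Protocol*

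**What the plan says.** Four parts of the protocol bear on this.

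- **Where the clinical parameters are recorded.** Section VIII, Outcomes Assessment, says that PI, GI, PD, BOP and CAL "will be recorded for each individual at 1 site at baseline and 3 months postoperatively". The site is not identified.
- **How PD is recorded.** Section VIII, a) Clinical Assessment, measures PD "at four points (mesio-facial, mid-facial, disto-facial and mid-lingual) to the nearest millimeter". For the facial readings the rule is: "The average of the three facial points will be recorded as the facial probing depth (FPD". The single mid-lingual reading is kept apart, as a lingual depth. The averaging rule is given for PD alone. CAL is measured from the CEJ to the depth of the pocket, with no points and no averaging specified.
- **Where GCF is taken.** The note to step 3 of the study procedures reads "Full mouth assessment will be done and then the deepest site will be evaluated for the GCF sample". Section VIII, b) says "Biochemical assessment will be done at the deepest pocket at baseline, and 3 months after non-surgical periodontal therapy".
- **What is to be analysed.** Aim 1 in section IV correlates changes in GCF Endocan and TNF-α "with changes in periodontal parameters after NSPT in both groups with clinical parameters". The primary outcome includes "probing depth and clinical attachment level comparing between hypertensive and non-hypertensive groups".

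No sentence says that the recorded clinical site is the GCF pocket, or that the sampled point's own depth is the PD value paired with the biomarker.

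**The concern.** Aim 1 is a question about one place in the mouth: does the biomarker change in a pocket go with the clinical change in that pocket? The GCF sample belongs to one pocket. When that pocket is facial, the PD value that the protocol tells the examiner to record is a mean over three points, two of which were not sampled. Unless the three points respond largely together, the other two add variation unrelated to the sampled fluid and pull the observed correlation towards zero. With 20 patients per group there is little room for that loss.

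This is a data-capture rule and not only an analysis choice. An analysis plan can use the sampled point's depth only if someone has written it down at both visits.

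**Working it through.** **Step 1. Which pockets are affected, on the most favourable reading.** Take the single recorded site to be the GCF-sampled pocket.

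| Position of sampled pocket | What the PD rule records |
|---|---|
| Mesio-, mid- or disto-facial | Mean of that point and two others |
| Mid-lingual | The pocket's own depth |
| Mesio- or disto-lingual | Nothing: not among the four points |

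The last row arises only if the full-mouth assessment probes more than these four points, which the protocol does not say.

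**Step 2. Size in one patient (assumed depths).** Facial readings of 5, 3, 3 mm fall to 3, 3, 3 mm.
- Sampled point: 5 − 3 = 2.0 mm.
- Facial mean: 11/3 − 9/3 = 3.67 − 3.00 = 0.67 mm, one third of the pocket's change.

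**Step 3. Effect on the correlation, facial pocket.** The protocol gives no SDs or correlations, so these inputs are assumptions: true correlation at the sampled point r = 0.60; SD of true PD change per point τ = 0.8 mm; probing-error SD per reading e = 0.3 or 0.5 mm; share of response variance common to the points ρ = 0 to 0.5. A change uses two readings, so its error variance is 2e².

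- Sampled point: r·τ / √(τ² + 2e²)
  - e = 0.3: 0.48 / √0.82 = 0.53
  - e = 0.5: 0.48 / √1.14 = 0.45
- Facial mean, with s = (1 + 2ρ)/3: r·τ·s / √(τ²s + 2e²/3)

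| ρ | s | e = 0.3 | e = 0.5 |
|---|---|---|---|
| 0 | 0.333 | 0.16/√0.273 = 0.306 | 0.16/√0.380 = 0.260 |
| 0.25 | 0.500 | 0.389 | 0.344 |
| 0.5 | 0.667 | 0.32/√0.487 = 0.459 | 0.32/√0.593 = 0.415 |
| 0.75 | 0.833 | 0.519 | 0.478 |

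For ρ from 0 to 0.5 the facial mean gives 0.26–0.46 against 0.45–0.53 for the sampled point.

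**Step 4. Where the order reverses.** Setting the two expressions equal gives s²(τ² + 2e²) = τ²s + 2e²/3.
- e = 0.3: s = 0.865, so ρ = (3 × 0.865 − 1)/2 = 0.80.
- e = 0.5: s = 0.755, so ρ = 0.63.
- Allowing for rounding to whole millimetres (variance 1/12 added per reading), the crossover falls to 0.69 and 0.59.

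Above these values the facial mean does slightly better, because averaging removes probing error. At ρ = 0.75 and e = 0.5 it gives 0.478 against 0.450.

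**Step 5. Power for the correlation.** Two-sided 0.05, Fisher z: power ≈ Φ(atanh(r)·√(n − 3) − 1.96), at full enrolment and with every sampled pocket facial.

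| n | Sampled point (r 0.45–0.53) | Facial mean (r 0.26–0.46) |
|---|---|---|
| 20 (one group) | 51–68% | 20–53% |
| 40 (pooled) | 84–95% | 37–85% |

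Mid-lingual pockets lose nothing, so a mixed sample lies between the two columns.

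**Step 6. A second, simpler model.** Ignore probing error and assume equal variances with a between-point correlation of 0.2 to 0.8. The correlation between one point and a three-point mean that contains it is √((1 + 2 × 0.2)/3) = 0.683 up to √((1 + 2 × 0.8)/3) = 0.931. A pocket-level correlation of 0.50 becomes 0.34–0.47, and the total n for 80% power rises from 30 to between 34 and 65. The direction is the same.

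**The case against.** The strongest reply is that the single recorded site is plainly the deepest, GCF-sampled one, since the protocol moves from full mouth to deepest site. That is the most coherent reading, and it reduces the unnamed site to a matter of clarification. It does not remove the averaging of a facial pocket's PD.

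A second reply is that the loss is hypothetical. All the inputs are assumed, the power ranges overlap, and three points on one tooth face under one treatment may respond largely together. This stands as a limit: the harm is conditional, and it reverses when most of the response is shared.

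A reader might also infer four stronger things that the protocol does not support:

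- **That the point readings are lost for good.** The protocol says what is recorded as the facial depth. It does not say that the readings behind it are discarded, and the full-mouth assessment must yield a depth for the deepest site at baseline. Loss is a risk, not a stated fact.
- **That lingual pockets suffer most because the facial mean leaves them out.** The mid-lingual depth is recorded separately, so that pocket keeps its own value.
- **That aim 1 as a whole is compromised.** The averaging rule is not stated for CAL, PI or GI.
- **That the primary between-group comparison is biased.** Both groups are measured by the same rule and no such harm has been shown. Which PD value enters that comparison may be settled in an analysis plan that is not at hand.

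**Conclusion.** The point holds in a limited form. As written, the PD rule does not give the depth of the sampled point when the deepest pocket is facial, and the protocol does not otherwise tie the recorded PD to the GCF pocket. For such pockets, the observable PD–biomarker correlation is 0.26–0.46 instead of 0.45–0.53 under the stated assumptions. There is no penalty once the shared part of the response exceeds about 0.6–0.8. The overall effect also depends on the proportion of deepest pockets that are facial, which the protocol does not give.

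This should be changed because it affects what aim 1 can show and must be settled before data collection. Naming the recorded site, and the PD value for the between-group comparison, is clarification only.

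**What to change.** In section VIII, a) Clinical Assessment:

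1. Record and keep each individual PD reading; the facial mean may stay as a further summary.
2. Mark the GCF-sampled point on the chart at baseline, including when it is not one of the four listed points.
3. Re-probe PD and CAL at that same point at 3 months.
4. State that aim 1 uses the change at that point.

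As clarification, say that the single recorded site is the GCF-sampled site, reconcile this with the full-mouth assessment in step 3, and name the PD value used for the comparison between hypertensive and non-hypertensive patients.

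The cost is close to nil. The four points are already probed, so the change amounts to writing down readings now summarised as a mean, marking one point on the chart, and adding a few sentences to the text. A pocket outside the four points needs one extra reading per visit.
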